9.2 SAMPLE SIZE DETERMINATION

Based on published literature, 50% of children will require repeat induction/treatment escalation by the end of the first year after diagnosis.⁴³⁻⁴⁵ 25 children carrying the high-risk microbiome signature will need to be randomized to each study arm (A1 or A2) (10% drop out assumed) in the larger trial following on from this pilot trial, assuming 80% power, to reduce the risk of flaring from 80% to 40%. These calculations are based on assumptions of relapse risk as no prospective microbiome data are available to inform this risk prediction of an unfavourable disease course.

In this pilot trial, 20 children will be enrolled to assess feasibility. The clinical data about relapse risk were not used to determine this sample size for the pilot trial. The 20 children of the pilot study will be allocated to either group A or group B, based on baseline microbiome data, unless the subject does not achieve clinical remission at week 4. If the subject does not achieve clinical remission (PCDAI less than or equal to 10) then the responsible physician can decide to start azithromycin/metronidazole for 8 weeks as additional induction therapy in Group C. Randomization will determine whether patients in group A, will be given SOC (A1) or SOC+antibiotics (A2).

9.3 POPULATIONS FOR ANALYSES

- Intention-to-Treat (ITT) Analysis Dataset will include all randomized participants: we will compare group A1 vs. group A2 for the primary analyses. In secondary/exploratory outcome analyses, we will compare the effects of treatment with antibiotics on the microbiome to assess whether indeed the signature of group A (A2) can be modified to move closer to group B. If this is the case, then (A2+B) vs. A1, will be compared. If the microbiome shifts associated with antibiotic use do not make A2 more similar to group B, then we will compare A1+B vs. A2 to assess whether there is an additional immune-regulatory effect of azithromycin (in combination with metronidazole) to influence disease flare risk. Group C samples will be analysed as a separate group in an observational study arm.
- Modified Intention-to-Treat Analysis Dataset will include participants who took the antibiotic intervention for at least 48 hours and had at least 6 months of follow-up outcome data.

- Safety Analysis Dataset will include participants who took at least 1 week of study intervention for whom safety analyses will be conducted
- Per-Protocol Analysis Dataset will include participants in the full analysis (ITT) set who took at least 2 weeks of study intervention during the treatment period and complied with the protocol sufficiently to ensure that these data would be likely to represent the effects of study intervention according to the underlying scientific model

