7 STUDY INTERVENTION DISCONTINUATION AND PARTICIPANT DISCONTINUATION/WITHDRAWAL

7.1 DISCONTINUATION OF STUDY INTERVENTION

Discontinuation of the antibiotic treatment between weeks 4 and 12 does not mean discontinuation of the study. A participant who discontinues the antibiotic intervention will be moved into the Group A control group (Group A1) and receive SOC, but these patients will not be included in the analysis of Group A1 to avoid selection bias as a patient who discontinues treatment in week 11 may differ from a patient who discontinued in week 5. Any patients discontinuing treatment will therefore be reported separately.

The remaining study procedures should be completed as indicated by the study protocol. If a clinically significant finding is identified (including, but not limited to changes from baseline) after enrollment, the investigator or qualified designee will determine if any change in participant management is needed. Any new clinically relevant finding will be reported as an adverse event (AE). Specific criteria for discontinuation due to known or potential AE associated with the study intervention are provided in section 7.2.

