9.4 STATISTICAL ANALYSES

9.4.1 GENERAL APPROACH

All summary tables will be presented by treatment group (Group A1, A2, and B) and, where applicable, by study visits. For descriptive statistics, continuous variables will be summarized with the mean, median, standard deviation, minimum and maximum. Categorical variables will be presented as counts and proportions expressed as a percentage. In addition, summary figures will be generated for longitudinal data to display change in mean or proportion over time.

Missing values in continuous variables will not be imputed. Missing values in categorical variables will be imputed as non-responders.

All tests will be two-sided and considered significant at $P<0.05$. Hypothesis tests that are not statistically significant will be deemed inconclusive. No adjustments to the test-wise error rate will be made.

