9.4.4 SAFETY ANALYSES

This study is not evaluating a formal safety outcome variable.

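### The only safety set requires a week on antibiotics, so a child who stops in week 1 because of an adverse event drops out of the safety denominator

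*Combined protocol and SAP*

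**What the plan says.** Section 9.3 defines four sets: ITT, modified ITT, Safety and Per-Protocol. The safety definition is: "Safety Analysis Dataset will include participants who took at least 1 week of study intervention for whom safety analyses will be conducted". It makes no exception for a child who stopped because of an adverse event. The modified ITT set, which is for efficacy, takes those who "took the antibiotic intervention for at least 48 hours and had at least 6 months of follow-up outcome data".

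Section 9.4.4 says only: "This study is not evaluating a formal safety outcome variable". It names no other safety population and does not say what will be tabulated in the Safety set.

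Section 7.1 says that a child who discontinues the antibiotics "will be moved into the Group A control group (Group A1) and receive SOC" but is left out of the A1 analysis, and adds: "Any patients discontinuing treatment will therefore be reported separately".

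On Group C, whose children are not in remission at week 4 and may receive the same antibiotics for eight weeks (4.1, 9.2), section 9.3 says "Group C samples will be analysed as a separate group in an observational study arm". Section 9.4.1 begins "All summary tables will be presented by treatment group (Group A1, A2, and B" and does not list Group C.

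**The concern.** A safety set should contain everyone exposed to the drug. A one-week minimum selects on tolerating the drug for a week, and early intolerance is part of what a safety summary has to show. The thresholds are also in an odd order, since safety needs longer exposure than modified ITT does.

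What is at stake is the descriptive rate of stopping for adverse events or intolerance. With 20 children enrolled and only some of them exposed, one child can decide whether that rate is zero. The rule could also outlast the pilot. The Netherlands addendum (section 12, on the full-scale trial) says that, if the pilot proves feasible, the protocol will be resubmitted without substantial change and pilot data can be carried over.

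A smaller gap sits beside it. A Group C child who takes the antibiotics for a week meets the wording of the Safety set, but the summary tables in 9.4.1 have no column for that child.

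**Working it through.** The plan gives no safety rate and no stopping rate, so there is no figure to reproduce. The check is a reading of the definitions, followed by arithmetic on assumed counts.

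**1. Exposure needed to enter each set (9.3)**

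| Set | Minimum antibiotic exposure |
|---|---|
| ITT | none (randomised) |
| Modified ITT | 48 hours, plus 6 months of outcome data |
| Safety | 1 week |
| Per-Protocol | 2 weeks, plus adequate compliance |

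The week is not defined further. It could mean seven calendar days or one five-day azithromycin block. A child who stops before completing it is out on either reading.

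**2. Does another section change the set?** Section 8.3.4 has all adverse events documented, 9.4.8 has data recorded individually, 7.1 reports discontinuers separately, and 10.1.6 has the DSMB look at each arm. All of these preserve the information. None of them alters who is in the Safety set. Section 7.2 lists adverse events that may lead to stopping, including allergic reaction, and attaches no minimum exposure to them.

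**3. Effect on a stopping rate.** Let E be the number exposed and T the number who ever stop for an adverse event. Let k be those of the T who stop in week 1, and m the children who stop in week 1 for another reason.

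- Any-dose set: T / E
- One-week set: (T − k) / (E − k − m)

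All counts below are assumed.

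| E | T | k | m | One-week set | Any-dose set |
|---|---|---|---|---|---|
| 10 | 1 | 0 | 0 | 1/10 = 10% | 1/10 = 10% |
| 10 | 1 | 1 | 0 | 0/9 = 0% | 1/10 = 10% |
| 10 | 1 | 0 | 1 | 1/9 = 11.1% | 1/10 = 10% |
| 10 | 2 | 1 | 0 | 1/9 = 11.1% | 2/10 = 20% |
| 5 | 1 | 1 | 0 | 0/4 = 0% | 1/5 = 20% |
| 15 | 1 | 1 | 0 | 0/14 = 0% | 1/15 = 6.7% |
| 25 | 3 | 1 | 0 | 2/24 = 8.3% | 3/25 = 12% |

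The last row uses the 25 per arm that 9.2 gives for the larger trial.

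An adverse-event stop in week 1 pushes the rate down, and a week-1 stop for another reason pushes it up. The effects are unequal: in rows 2 and 3, one child moves the rate by 10 points downward but by only 1.1 points upward.

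**4. Other summaries.** For the share of children with any adverse event, the effect is small when events are common. With 8 of 10 affected, one of them a week-1 stopper, the set shows 7/9 = 78% instead of 8/10 = 80%.

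**5. Precision.** Exact (Clopper-Pearson) 95% intervals are 0 to 33.6% for 0/9 and 0.3 to 44.5% for 1/10. They overlap almost entirely.

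**6. Chance that the rule bites.** If each exposed child has probability p of stopping in week 1 for an adverse event, the chance that at least one is excluded is 1 − (1 − p)^E. For assumed p of 5%, 10% and 15%, this is 23%, 41% and 56% with E = 5, and 40%, 65% and 80% with E = 10.

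**The case against.** The strongest reply is that nothing depends on this set. There is no formal safety outcome, no section ties a table to the Safety set, and 7.1 reports every discontinuer separately whatever the time on drug. A week-1 stopper should therefore appear somewhere in the report. This largely stands, and it limits the harm to a denominator. It does not remove the defect: 9.3 itself says that safety analyses will be done in this set, and 7.1 gives selection bias in the A1 analysis as its reason, not safety.

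Four stronger readings are tempting, and the documents do not support them.

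- *The rate is biased low whenever a child stops in week 1.* Section 7.2 lets participants leave for any reason. A week-1 stop unrelated to an adverse event removes only a denominator count and raises the rate.
- *The plan expects stops in the first week.* Section 7.1 remarks that "a patient who discontinues treatment in week 11 may differ from a patient who discontinued in week 5". With a week-4 start, week 5 may fall within the first week on drug or just after it. Section 2.3.1 says which azithromycin side effects led to discontinuation, but not when.
- *Group C is ignored for safety.* Section 9.3 calls it a separately analysed observational arm, and the DSMB covers each arm. The gap is narrower: 9.3 speaks of samples, and 9.4.1 gives Group C no column.
- *Everything needed for a Group C table is already collected.* Adverse events are. Calendar-based exposure is less certain: the schedule (1.3) makes calendar teaching conditional, 4.1 gives the instructions to A2, and 6.4 assigns the calendar to the antibiotic treatment arm.

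It is also fair to say that carry-over to a full-scale trial is conditional, and that the set could be redefined then without loss of data.

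**Conclusion.** The point holds as a wrong definition in 9.3, not as a loss of safety data. The only safety set excludes any child with less than a week on antibiotics, whatever the reason for stopping. A rate of stopping for adverse events computed in it is understated when a week-1 stop is due to an adverse event and slightly overstated when it has another cause. It is unaffected if nobody stops in week 1.

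The size rests on assumed counts, because the documents give neither the number exposed nor a stopping rate. The consequence is confined to descriptive rates in a 20-child pilot, and those rates are imprecise under either definition. No test and no primary conclusion changes. Severity is minor to moderate; the case for acting is that the correction costs almost nothing.

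**What to change.** **Main change (9.3).** Define the Safety set as all participants who took at least one dose of study antibiotic (A2 or C), summarised by treatment received. State in 9.3 or 7.1 that, for safety, a participant who discontinues is counted in the group in which the antibiotic was taken. The separate report of discontinuers and the efficacy handling in 7.1 stay as they are.

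**Secondary change (9.4.1, 9.4.4).** Add a descriptive column for Group C adverse events and antibiotic discontinuations, without tests and not pooled with A2. These children are not in remission at week 4, and the intolerance symptoms predefined in 6.1.2 overlap with active disease. Before tabulating Group C exposure from the calendar, reconcile 1.3, 4.1 and 6.4 on whether Group C completes it.

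These are counting rules for tables and change no clinical rule.

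**Cost.** A short wording amendment, which needs IRB approval under the Statement of Compliance, and one more table column. Adverse events are already reviewed for all groups at weeks 4, 12, 24, 36 and 52. The downside is that descriptive rates may look slightly less favourable, and a column of a few children will be imprecise.

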9.4 STATISTICAL ANALYSES

9.4.1 GENERAL APPROACH

All summary tables will be presented by treatment group (Group A1, A2, and B) and, where applicable, by study visits. For descriptive statistics, continuous variables will be summarized with the mean, median, standard deviation, minimum and maximum. Categorical variables will be presented as counts and proportions expressed as a percentage. In addition, summary figures will be generated for longitudinal data to display change in mean or proportion over time.

Missing values in continuous variables will not be imputed. Missing values in categorical variables will be imputed as non-responders.

All tests will be two-sided and considered significant at $P<0.05$. Hypothesis tests that are not statistically significant will be deemed inconclusive. No adjustments to the test-wise error rate will be made.

9.4.3 ANALYSIS OF THE SECONDARY OUTCOME VARIABLE(S)

In secondary outcome analyses, the effects of treatment with antibiotics on the microbiome will be assessed to determine whether the signature of group A2 can be modified to move closer to group B.

If this is the case, then groups A2 and B will be pooled and compared against A1. If the microbiome shifts associated with antibiotic use do not make A2 more similar to group B, then groups A1 and B will be pooled and compared against A2 to assess whether there is an additional immune-regulatory effect of azithromycin (in combination with metronidazole) to influence disease flare risk.

Data for secondary outcome variable analysis are independent of the primary outcome variable and will be collected at each study visit.

Continuous secondary outcomes will be summarized at each visit for both the observed values and the changes from baseline. A linear mixed model with timepoint, group, their interaction and baseline as covariates will be used to assess the difference in means between groups at each timepoint. An AR(1) covariance structure will be assumed and the Kenward-Roger degrees of freedom approximation will be utilized. Least squares estimates for the population mean and standard deviation will be provided at each assessment timepoint by group. Missing values will not be imputed. Due to the exploratory nature of the assessments, no correction for multiplicity will be made.

Categorical secondary outcomes variables will be analyzed similarly to the primary outcome (Section 9.4.2).

The analysis of the secondary efficacy parameters will be based on the ITT population.

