3 OBJECTIVES AND OUTCOME VARIABLES

OBJECTIVES	OUTCOME VARIABLES	JUSTIFICATION FOR OUTCOME VARIABLES
Primary		
To evaluate the potential efficacy of personalized adjunctive antibiotic therapy in maintaining clinical remission in pediatric subjects undergoing SOC induction therapy for mild to moderate Crohn's disease who have a relapse-associated microbiome profile	Proportion of subjects in sustained remission at 52 weeks after starting standard of care induction therapy Sustained remission is defined PCDAI less than or equal to 10 AND no need of re-induction for clinical flare (new course of EEN, need to restart steroids), no steroid dependence, no biologic (anti-TNF) use, and no intestinal surgery by 12 months.	We will aim to demonstrate superiority of adjunctive antibiotic therapy + SOC over SOC alone in patients with a relapse-associated microbiome. Group A1 and A2 will be compared and sustained remission is the principal analysis variable.
Secondary		

OBJECTIVES	OUTCOME VARIABLES	JUSTIFICATION FOR OUTCOME VARIABLES
To evaluate the potential efficacy of personalized adjunctive antibiotic therapy in improving PRO, components of established disease activity measures in remission, as well as 'biochemical' remission in pediatric subjects undergoing SOC induction therapy for mild to moderate Crohn's disease who have a relapse-associated microbiome profile	
Longitudinal (clustered and with respect to baseline) changes in disease activity indices (PCDAI) components, and inflammatory markers in blood and stool:
 
 • PCDAI score (0-100) • Normalization of CRP (mg/dL) • Fecal calprotectin (FCP) (microgram/g) 
Longitudinal (clustered and with respect to baseline) changes PRO:
 
 • IMPACT (self-report, ages 9-17 years) 	Multiple secondary variables are needed to describe clinically relevant treatment benefits. Depending on the results of the microbiome analysis, either groups A2 and B will be pooled and compared with group A1 or groups A1 and B will be pooled and compared with group A2 (section 9.4.3).
Tertiary/Exploratory		

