4.2 SCIENTIFIC RATIONALE FOR STUDY DESIGN

The experimental treatment arm (Group A2) will receive an add-on therapy given on top of existing SOC induction therapy and the control groups will receive SOC induction therapy alone. This will be a superiority study to demonstrate that add-on antibiotic therapy is superior to existing standard of care.

The control arms (Group A1 and B) are stratified based on microbiome profile. This will allow us to confirm our previous observations that subjects with a relapse-associated microbiome profile are at an increased risk of relapse after completing induction therapy. The primary objective will be to compare the rates of sustained remission between Groups A1 and A2 to determine whether add-on antibiotic therapy improves outcomes for patients with a relapse-associated microbiome profile. Group C will allow patients to receive additional antibiotic for a separate indication of induction of remission, as this group has not received clinical remission on nutritional therapy alone by week 4.

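### Secondary analyses pool the non-randomized Group B with A2 or A1, as a post-treatment microbiome result dictates, so neither pooled contrast estimates an antibiotic effect

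*Combined protocol and SAP*

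**What the plan says.** Section 9.4.3 sets a two-way rule for the secondary outcomes. The antibiotic-treated arm A2 is first examined to see whether its microbiome has moved towards Group B. "If this is the case, then groups A2 and B will be pooled and compared against A1". If it has not, "then groups A1 and B will be pooled and compared against A2 to assess whether there is an additional immune-regulatory effect of azithromycin". The rule also appears in section 9.3, in the section 3 table ("either groups A2 and B will be pooled and compared with group A1", or the alternative) and in the adapted table of the Netherlands addendum (section 12).

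Other parts of the plan that bear on it:

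- **How B arises.** Section 4.1 assigns children to A or B by the posterior probability of a relapse-associated microbiome at baseline. Only A is randomized. B continues on standard of care alone.
- **Expected prognosis.** Section 4.2 sets out to confirm that "subjects with a relapse-associated microbiome profile are at an increased risk of relapse after completing induction therapy".
- **Analysis set.** "The analysis of the secondary efficacy parameters will be based on the ITT population" (9.4.3), and "Intention-to-Treat (ITT) Analysis Dataset will include all randomized participants" (9.3).
- **Objective.** The secondary objective in section 3 concerns children who have a relapse-associated profile.
- **Testing.** "All tests will be two-sided and considered significant at" P<0.05 (9.4.1). "Due to the exploratory nature of the assessments, no correction for multiplicity will be made" (9.4.3).
- **Primary analysis.** Section 9.4.2 compares A1 with A2 by Fisher's exact test, without pooling.

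**The concern.** The two contrasts fail in different ways. A2+B versus A1 is not an antibiotic comparison, because the B children on the supposed antibiotic side never took any; B's better prognosis is credited to the drugs. A1+B versus A2 does compare no antibiotics with antibiotics, but it is confounded by the very variable that defines A and B, so B's prognosis counts against the drugs.

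Three further problems need no arithmetic:

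- The branch is chosen by a post-treatment result, and section 9.4.3 gives no distance measure, visit or cut-off for having moved closer. The contrast can be settled after the data are seen.
- The ITT set contains only randomized children, so it excludes B. The pooled analysis cannot be run on the set named for it.
- B children lack the relapse-associated profile, so they fall outside the secondary objective.

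Section 3 gives the pooled contrasts as the comparison for the secondary outcomes, and section 9.4.3 never names A1 versus A2 for them. At stake is a secondary result that shows benefit or harm when antibiotics do nothing, or that hides a real effect. Section 12 foresees resubmitting the protocol without substantial changes if the pilot is feasible, and allows pilot data into the full trial.

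**Working it through.** **The plan's own figure.** Section 9.2 gives 25 per arm for flare risks of 80% and 40%, 80% power and 10% dropout. The two-sided pooled-variance formula gives n = [1.96·√(2·0.6·0.4) + 0.842·√(0.8·0.2 + 0.4·0.6)]² / 0.4² = 22.3, so 23. Then 23/0.9 = 25.6, so 26, which is within one of the stated 25. Exact Fisher power with 25 evaluable per arm is 78.8%.

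**Bias formula.** Let w = nB/(nA + nB) be B's share of the pool, where nA is the size of the arm pooled with B. On any mean or risk scale:

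- (A2+B) − A1 = true effect + w·(B − A2)
- A2 − (A1+B) = true effect + w·(A1 − B)

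With no antibiotic effect, A1 = A2. Each contrast is then off by w times the A-to-B gap, in opposite directions. Sample size does not enter except through w.

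**Assumed sizes.** 25/25/50 in A1/A2/B for a full trial (the 25s are the plan's, the 50 is an assumption), so w = 50/75 = 2/3. For the 20-child pilot several splits are shown.

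**Continuous outcomes (PCDAI, CRP, calprotectin, IMPACT).** The documents give no A-to-B gap, so gaps of 0.3, 0.5 and 0.8 SD are assumed. The bias is 2/3 of each: 0.20, 0.33 and 0.53 SD. With no antibiotic effect, a simulated two-sample t-test at one visit declares a false benefit for A2+B versus A1 in about 13%, 28% and 59% of trials at 25/25/50, and in about 5%, 8% and 14% at 5/5/10.

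**Flare scale, as an illustration.** Section 9.2 gives 50% overall and 80% in high-risk children. If both apply and a proportion q carries the signature, B's flare risk is (0.5 − 0.8q)/(1 − q): 37%, 30% and 20% for q = 0.3, 0.4 and 0.5. A fourth case sets B at 50%. Rejection rates come from exact enumeration of the two-sided Fisher test at 0.05, counted by direction.

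No antibiotic effect, 25/25/50:

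| B flare risk | A2+B flare risk | False difference from A1 (80%) | A2+B vs A1 declares benefit |
|---|---|---|---|
| 37% | 51.4% | 29 points | 72% |
| 30% | 46.7% | 33 points | 85% |
| 20% | 40.0% | 40 points | 95% |
| 50% | 60.0% | 20 points | 41% |

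A1+B versus A2 declares false harm at the same rates. A1 versus A2 declares false benefit in 1.1%. If B is sized to match q (117, 75 and 50 children), the first three rates become 92%, 94% and 95%.

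Planned effect (A2 at 40%, true difference −40 points), A1+B versus A2, 25/25/50:

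| B flare risk | Expected difference | Declares benefit |
|---|---|---|
| 37% | 40 − 51.4 = −11 points | 13% |
| 30% | 40 − 46.7 = −7 points | 6% |
| 20% | 40 − 40 = 0 points | 1.5% |
| 50% | 40 − 60 = −20 points | 35% |

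A1 versus A2 declares benefit in 79%.

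Pilot splits, no antibiotic effect, A2+B versus A1 declares benefit:

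- 5/5/10, B at 20%, nobody in C: 23%
- 4/4/12, B at 30%: 10%
- 3/3/14, B at 37%: 7%
- 4/4/8 with four in C, B at 20%: 7%; with B at 30%: 3%

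**The case against.** The strongest reply is that these are exploratory analyses in a feasibility pilot. The randomized primary test stands apart, tables are shown separately for A1, A2 and B (9.4.1), non-significant results are to be called inconclusive (9.4.1), and section 12 concedes that the numbers cannot support efficacy conclusions. All of this is true and limits the harm in the pilot. It does not change what the pooled contrasts estimate, and their tests are still declared significant at P<0.05.

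Several points about size also stand:

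- The false-benefit and false-harm rates belong to mutually exclusive branches. Each holds when its branch is taken; the chance of each branch is not modelled, so they are not error rates of the whole plan.
- Flare is not a listed secondary outcome (9.1), although sections 9.3 and 9.4.3 give flare risk as the purpose of the second contrast. The flare figures only illustrate the scale.
- The t-test is not the planned mixed model, whose baseline covariate may absorb part of the gap. That covariate is the outcome's own baseline, not the microbiome stratum, and categorical outcomes get no adjustment. If the stratum were added, B would have no comparator within its stratum and would add nothing to the estimated treatment difference.
- Carry-over into a full trial is permitted, not automatic, and needs approval.

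Two readings of the text soften the point. Categorical outcomes are to be analysed like the primary one, which suggests A1 versus A2, and a mixed model with a group term could yield that contrast. But section 3 states the pooled comparison outright, and the pooling paragraph is not confined to one type of outcome. Section 8.1 does set a posterior-probability cut-off of 30% for the unfavourable signature, but section 9.4.3 does not use it to define a move towards B.

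Finally, the pooled contrasts could be kept and relabelled as non-causal associations. That would prevent misreading, but it would leave contrasts that answer no stated objective.

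**Conclusion.** The concern holds. Both pooled contrasts combine the antibiotic effect with a prognostic difference that the trial itself presumes. With no antibiotic effect they are unbiased only if A and B have the same prognosis, which contradicts section 4.2. The conflicts with the ITT set and the secondary objective, and the undefined selection rule, hold whatever the numbers.

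The size depends on assumptions: 50 children in B, the A-to-B gaps, and flare rates carried over from section 9.2. The 50% rate there refers to the first year after diagnosis, whereas children up to 36 months from diagnosis are eligible. Groups A and B also exclude children not in remission at week 4, which could narrow the gap. On these assumptions the distortion is large at full-trial size and modest in the pilot. The primary analysis and the by-group summaries are sound.

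**What to change.** Delete both pooling branches in sections 3, 9.3, 9.4.3 and 12. State that A1 versus A2, on the ITT set of randomized children, is the only treatment contrast for every secondary outcome, continuous and categorical. Keep B as a separate, unpooled group with two uses: A1 versus B for the prognostic question in section 4.2, and the A2-to-B microbiome distance, with its measure and visit stated in advance, as a descriptive exploratory result.

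This needs no new data or visits. Because the text is in the protocol, it needs an amendment with IRB review (Statement of Compliance). The treatment contrast will contain fewer children, but the children lost carry no information on the antibiotic effect in the target population.
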